2.6 Statistical Analysis

Statistical analysis was performed using Graphpad Quick Calcs (GraphPad version 6.04 for Windows, GraphPad Software, La Jolla California USA). Baseline comparisons were performed using chi-square tests and T-tests. Continuous variables are expressed as mean \pm standard deviation (SD). Differences between preoperative and postoperative parameters were compared by Wilcoxon paired rank test. For all tests, a two-sided $p < 0.05$ was considered statistically significant.

Sample size

THIS IS A CONTROLLED RANDOMIZED STUDY OF BINARY NON-INFERIORITY OUTCOME IN PARALLEL GROUPS. IF THERE IS TRULY NO DIFFERENCE BETWEEN THE STANDARD AND EXPERIMENTAL TREATMENT, THEN 138 PATIENTS ARE REQUIRED TO BE 90% SURE THAT THE LOWER LIMIT OF A ONE-SIDED 95% CONFIDENCE INTERVAL (OR EQUIVALENTLY A 90% TWO-SIDED CONFIDENCE INTERVAL) WILL BE ABOVE THE NON-INFERIORITY LIMIT OF -10. SAMPLE SIZE WAS CALCULATED WITH SEALED ENVELOPE LTD. 2012.

Appendix 2

Chief Investigator: [name], PhD – UOC Chirurgia Generale – Ospedale A. Rizzoli –

Lacco ameno napoli. [contact]; cellulare: [name].

Results summarized in the table:

Table 1 :Preoperative demographics data

Table 2: Weight, Body mass index, and the percentage of excess body weight loss and the Percentage Total Weight loss of the two groups at follow-up 3-6-12-24-months

Table 3: GERD Health-Related Quality-of-Life (GERD-HRQL) Score preoperative and postoperative scores follow-up 3-6-12-24 months

Table 4: Endoscopy Preoperative and at 1 and 2 years follow-up into two Groups

Table 1 Preoperative demographics data

Patients	Total	Group A (n=75)	Group B(n=75)
Age	33.6 ± 14	32.2 ± 8	34.2 ± 9
Male	39%	35%	38%
Female	61%	63%	62%
Height	151.2 ± 22	150.1 ± 23	152.8 ± 33
Weight kg	121.9 ± 21.7	124.5 ± 26.7	125.3 ± 23.5
BMI	44.23 ± 6.32	43 ± 8 (40–57)	44 ± 4(40–55)
ASA(I-II)(%)	65%	64%	66%
ASA(III-IV)(%)	35%	36%	34%
T2MD(%)	12(8.%)	7(9.3%)	5(6.6%)
Chronic obstructive pulmonary disease(%)	7(4.6%)	2(2.6%)	3(4%)
Heart Ischemia	1	0	0
Hypertension(%)	95(63%)	55(73.3%)	40(53.4%)

BMI body mass index, %EWL percentage excess weight loss, %TWL percentage total weight loss, Type 2 Mellitus Diabetes (T2MD)

Table 2: Weight, Body mass index, and the percentage of excess body weight loss and the Percentage Total Weight loss of the two groups at follow-up

Patients	3 months follow-up		p	6 months follow-up		p	12 months follow-up		p	24 months follow-up		p
	145/150			141/150			136/150			131/150		
	Group A (n=72)	Group B(n=73)	p>0.05	Group A(n=70)	Group B(n=71)	P<0.05	Group A(n=67)	Group B(n=69)	p	Group A(n=65)	Group B(n=66)	p>0.05
BMI	30.9 ± 5.32	34.7 ± 4.18	P<0.05	26.13 ± 7.32	31.06 ± 3.12	P<0.05	24.2 ± 3.4	27.5 ± 4.3	P<0.05	25.2 ± 4.4	26.2 ± 3.3	p>0.05
EBWL%	40.9 ± 8.1	31.60 ± 8.7	P<0.05	54.1 ± 11.3	48.20 ± 12.5	P<0.05	63.7 ± 14.1	59.6 ± 12.5	P<0.05	62.8 ± 13.1	61.6 ± 10.5	p>0.05

Results

Table 3 GERD Health-Related Quality-of-Life (GERD-HRQL) Score preoperative and postoperative scores

Patients	Preoperative 150/150		3 months follow-up 145/150		p >0.05	6 months follow-up 141/150		P <0.05	12 months follow-up 136/150		P <0.05	24 months follow-up 131/150		p >0.05
	Group A (n=75)	Group B (n=75)	Group A (n=72)	Group B (n=73)		Group A (n=70)	Group B (n=71)		Group A (n=67)	Group B (n=69)		Group A (n=65)	Group B (n=66)	
GERD HRQL Score<15			38(52.7%)	57(78%)	P <0.05	36(51.4%)	56(78.8%)	P <0.05	47(70.4%)	55(79.7%)	P <0.05	49(75.3%)	55(83.3%)	P <0.05
GERD HRQL Score >16<30	7(9.3%)	9(12%)	29(40%)	15(20.5%)	P <0.05	30(42.8%)	14(19.7%)	P <0.05	16(23.8%)	13(18.8%)	P >0.05	14(21.5%)	10(15.1%)	P >0.05
GERD HRQL Score >31	-	-	5(6.9%)	1(1.3%)	P <0.05	4(5.7%)	1(1.4%)	P <0.05	4(5.9%)	1(1.4%)	P <0.05	1(1.5%)	0	P <0.05
Significant Vomit	-	-	11(15,3%)	3(4.1%)	P <0.05	6(8.6%)	2(2.8%)	P <0.05	6(8.9%)	2(2.9%)	P <0.05	2(3.1%)	1(1.5%)	P <0.05
Intolerance to food	-	-	2(2.7%)	0	P <0.05	1(1.4%)	0	p >0.05	0	0	p >0.05	0	0	p >0.05

Table 4: Endoscopy Preoperative and at 1 and 2 years follow-up into two Groups

	Preoperative Patients 150		1 year follow-up Patients 108/150(72%)		2 years follow-up Patients 105/150(70%)	
	Group A 75	Group B 75	Group A 53	Group B 55	Group A 52	Group B 53
Esophagitis						
A	4(5.3%)	5(6.7%)	9(16.9%)	7(12.7%)	5(9.6%)	5(9.4%)
B	-	-	11(20.7%)	5(9%)	9(17.3%)	3(5.6%)
C	-	-	2(3.8%)	0	1(1.9%)	0
D	-	-				
Esophageal biopsy						
Metaplasia	-	-	0	0	0	0
Helicobacter Pylori	9(12%)	7(9.3%)				
Hiatal Hernia< 5 cm	1(1.3%)	2(2.7%)	-	-	-	-

Figure 1 Diagram of Patients eliability

Flow Diagram

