Study Protocol

“Does Antrum Size Matter in Sleeve Gastrectomy?”

Study Protocol

“Does Antrum Size Matter in Sleeve Gastrectomy? ”

BACKGROUND

Laparoscopic sleeve gastrectomy (LSG) is currently the most frequent primary bariatric procedure performed worldwide. LSG is safe and effective in terms of excess weight loss. It is a powerful metabolic operation that activates significant hormonal pathways that lead to changes in eating behavior, glycemic control and intestinal functions. LSG can be a faster procedure for its technical aspects (any need for intestinal anastomosis, being limited to the stomach transection). The most frequent and sometimes dangerous complications are leaking, hemorrhage, splenic injury, stenosis and Gastroesophageal Reflux Disease (GERD)(1). Despite its established efficacy and safety, dispute still exists on optimal operative technique for LSG: bougie size, distance of resection margin from the pylorus, the shape of section at the gastroesophageal junction, staple line reinforcement and intraoperative leak testing are among the most controversial issues (2). Indeed, different Authors have adopted a resection distance from the pylorus between 2 and 6–7 cm with various reasons (3). In favor of resections more distant to the pylorus, Authors argue that it seems to improve gastric emptying, prevent distal stenosis and reduce intraluminal pressure, potentially leading to a lower incidence of fistula and/or reflux. On the other hand, resections close to the pylorus seems to reduce more the gastric distensibility and increase intragastric pressure, potentially leading to a better satiation with less oral intake (4, 5). However, only few studies have investigated the differences between these two approaches (3). Thus, the primary aim of this randomized monocentric study is to evaluate variations in percentage of excess weight loss (%EWL) at 1 and 2 years follow-up after LSG in subject with a gastric resection starting from 2 cm from the pylorus (wide antrectomy) compared to those with a gastric resection starting from 6 cm from the pylorus (small antrectomy). Secondary aim-points are represented by evaluation of differences in morbidity, mortality, tolerance to food, incidence of reflux symptoms and GERD Health-Related Quality-of-Life (GERD-HRQL) score between the two groups.

Material and Methods

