2.2 Study Design

The study is designed as a randomized controlled trial. Primary outcome was the evaluation of %EWL between 2 groups. Secondary outcomes were evaluation of morbidity, mortality, incidence of reflux symptoms and Quality of Life score between the Groups.From January 2015 to November 2017, a series of 218 consecutive patients suffering from morbid obesity and scheduled for LSG were included; informed consent was obtained from each participant before surgery.

Inclusion criteria were morbid obesity defined as BMI 40 kg/m² and age between 25–50 years old. Obesity-related comorbidities included Type 2 Mellitus Diabetes (T2MD), hypertension, hyperlipidemia, bronchial asthma, osteoarthritis and degenerative joint disease.

Exclusion criteria

Patients with previous bariatric surgical procedures, endocrine disorders causing obesity (as hypothyroidism and Cushing disease), pregnancy or lactation, psychiatric illness, or recent diagnosis of malignancy, inflammatory bowel disease, Barrett's esophagus, and GERD with esophagitis scored as or greater than grade B, a large hiatal hernia (>3 cm) were excluded from the study. In case of absence or grade A esophagitis, GERD was also considered as severe with GERD-HRQL > 30 and when interfering with daily activities or inducing dietary restriction despite, also these were excluded.

One hundred-fifty patients were considered eligible and randomized in two Group (Group A n = 75, Group B n=75). All patients underwent elective laparoscopic LSG. In the case of conversion to open surgery, patients were excluded. Details of enrollment procedure are shown in Fig. 1.

Randomization

Participants were randomly assigned to one of the two groups using computer-generated permuted blocks (www.randomization.com). Outpatient clinic controls were done by surgeons/surgical residents/GP blinded for the groups. Patients were randomized into 2 groups based on the distance to pylorus of resection: Group A (n=75) at 2 cm, Group B(n=75) at 6 cm. Results were obtained at 1 and 2 years follow-up. The randomization scheme was generated using the web site Randomization.com (<http://www.randomization.com>).

Blinding Process

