2.5 Post-operative evaluation

All patients were actively clinical followed up regularly at 3, 6, 12 and 24, included GERD-HRQL. UE was performed in all patients at 12 or 24 months. Significant vomiting and food intolerance were evaluated at 6, 12 and 24 months follow-up. Vomiting was considered significant when occurring at least three times a week and food intolerance was defined as vomiting occurring almost each day. Esophageal biopsies were performed only in case of esophagitis \geq B (9).

Weight loss parameters were recorded at 3, 6, 12 and 24 months after the LSG : BMI (in kg/m²), %EWL and percentage total weight loss %TWL from baseline. The secondary endpoints were GERD and esophagitis studied with Upper endoscopy and GERD score

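### Section 2.6 assigns no between-group test or effect estimate to postoperative %EWL, the primary outcome, and the 12-month P<0.05 label is not reproduced by a two-sided two-sample t-test on the printed summaries

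*Combined protocol and SAP*

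**What the plan says.** The Background section sets the primary aim: to "evaluate variations in percentage of excess weight loss (%EWL) at 1 and 2 years follow-up after LSG", for resection starting 2 cm versus 6 cm from the pylorus. Section 2.2 repeats it: "Primary outcome was the evaluation of %EWL between 2 groups". Section 2.5 shows that the measure is already a change; it records "EWL and percentage total weight loss %TWL from baseline".

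Section 2.6 assigns tests in two sentences. The first is "Baseline comparisons were performed using chi-square tests and T-tests". The second is "Differences between preoperative and postoperative parameters were compared by Wilcoxon paired rank test". A general rule follows: "For all tests, a two-sided $p < 0.05$ was considered statistically significant".

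Under the Sample size subheading the design is described differently: "THIS IS A CONTROLLED RANDOMIZED STUDY OF BINARY NON-INFERIORITY OUTCOME IN PARALLEL GROUPS". That paragraph uses a one-sided 95% interval and a limit of -10. It does not identify the binary endpoint, the reference group or the unit of the limit.

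Tables 2 and 3 print Group A versus Group B significance labels at each visit without naming a test.

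**The concern.** A two-arm trial needs a stated method for comparing the arms on its primary outcome. Here the named between-group tests are confined to baseline, and the one named postoperative test compares patients with themselves. A paired test does not compare Group A with Group B. Nor does it fit %EWL, which is measured from baseline and so has no preoperative value to pair with.

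The reader therefore cannot tell which test produced the printed labels, whether it was one- or two-sided, or what effect estimate goes with it. This matters most at 12 months, which is half of the primary aim and is presented as a significant difference. If that label depends on an unstated choice of test, so does the claim.

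**Working it through.** **Does any part of the protocol supply the missing test?**

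| Source | Method | Compares A with B? | Covers postoperative %EWL? |
|---|---|---|---|
| 2.6, first test sentence | chi-square, t-test | yes | no, baseline only |
| 2.6, second test sentence | paired Wilcoxon | no, within patient | no, nothing to pair |
| 2.6, significance rule | two-sided 0.05 | names no test | names no test |
| Sample size | one-sided 95% limit, margin -10 | yes | no, binary outcome, unnamed |

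No other section fills the gap.

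**Are the Table 2 labels reproduced?** Inputs are the printed means, SDs and group sizes. The test is Welch's two-sample t-test, with SE = √(SD_A²/n_A + SD_B²/n_B) and t = (mean_A − mean_B)/SE.

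| Outcome | Month | Group A | Group B | A − B | Two-sided p | Printed label | Agrees? |
|---|---|---|---|---|---|---|---|
| %EWL | 3 | 40.9 ± 8.1 (72) | 31.6 ± 8.7 (73) | 9.3 | <0.001 | P<0.05 | yes |
| %EWL | 6 | 54.1 ± 11.3 (70) | 48.2 ± 12.5 (71) | 5.9 | 0.0038 | P<0.05 | yes |
| %EWL | 12 | 63.7 ± 14.1 (67) | 59.6 ± 12.5 (69) | 4.1 | **0.075** | P<0.05 | **no** |
| %EWL | 24 | 62.8 ± 13.1 (65) | 61.6 ± 10.5 (66) | 1.2 | 0.56 | p>0.05 | yes |
| BMI | 3 | 30.9 ± 5.32 (72) | 34.7 ± 4.18 (73) | −3.8 | <0.001 | P<0.05 | yes |
| BMI | 6 | 26.13 ± 7.32 (70) | 31.06 ± 3.12 (71) | −4.93 | <0.001 | P<0.05 | yes |
| BMI | 12 | 24.2 ± 3.4 (67) | 27.5 ± 4.3 (69) | −3.3 | <0.001 | P<0.05 | yes |
| BMI | 24 | 25.2 ± 4.4 (65) | 26.2 ± 3.3 (66) | −1.0 | 0.144 | p>0.05 | yes |

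The 12-month %EWL row in full:

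- SE = √(14.1²/67 + 12.5²/69) = √(2.967 + 2.264) = 2.287, with 131 degrees of freedom.
- t = 4.1/2.287 = 1.79, two-sided p = 0.0754 (pooled-variance test 0.0748).
- 95% CI = 4.1 ± 1.978 × 2.287 = 4.1 ± 4.52, or −0.42 to 8.62. At these SDs and numbers a difference of about 4.5 would be needed for p<0.05.
- Most favourable rounding of every input (63.75 versus 59.55, SDs 14.05 and 12.45): p = 0.068 (pooled 0.067).
- One-sided p = 0.0754/2 = 0.038.

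At 24 months SE = 2.076 and the 95% CI is −2.9 to 5.3.

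**Are the Table 3 labels reproduced?** Fifteen cells carry P<0.05. Two-sided Fisher's exact and uncorrected chi-square tests both support five: score <15 and score 16–30 at 3 and 6 months, and vomiting at 3 months. Neither supports the other ten:

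| Cell | A | B | Fisher p | Chi-square p |
|---|---|---|---|---|
| 3 mo, >31 | 5/72 | 1/73 | 0.116 | 0.092 |
| 3 mo, food intolerance | 2/72 | 0/73 | 0.245 | 0.152 |
| 6 mo, >31 | 4/70 | 1/71 | 0.209 | 0.167 |
| 6 mo, vomiting | 6/70 | 2/71 | 0.166 | 0.140 |
| 12 mo, <15 | 47/67 | 55/69 | 0.237 | 0.198 |
| 12 mo, >31 | 4/67 | 1/69 | 0.205 | 0.161 |
| 12 mo, vomiting | 6/67 | 2/69 | 0.162 | 0.133 |
| 24 mo, <15 | 49/65 | 55/66 | 0.287 | 0.261 |
| 24 mo, >31 | 1/65 | 0/66 | 0.496 | 0.312 |
| 24 mo, vomiting | 2/65 | 1/66 | 0.619 | 0.550 |

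One-sided testing rescues at most one of the ten: 3 months, >31, by chi-square (0.092/2 = 0.046). One-sided Fisher values run from 0.10 to 0.50. The 24-month score bands sum to 64 of 65 and 65 of 66. Adding the unclassified patient in each group to either band leaves Fisher p at 0.195–0.388 for <15 and 0.244–1.0 for >31.

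**The case against.** The strongest reply is that the t-test is listed, a two-sided level is set for all tests, and a t-test agrees with seven of the eight Table 2 labels. Perhaps the t-test was used throughout and its scope was badly described. That is plausible, and for this reason a reader who infers that the plan cannot test its primary outcome goes too far: the documents show only that no test is assigned to it. If the t-test was used, however, the 12-month label does not follow from the printed figures.

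A reader might also infer that the 12-month label is simply wrong, or that a one-sided test was run. Neither is established. An unpaired rank test on raw data could give a different p-value and cannot be checked from summaries. One-sided testing would contradict the protocol's own rule. A mean or SD could also be misprinted, because the printed summaries do not fit one another well. Mean BMI in Group A goes from 43 (Table 1) to 24.2 at 12 months. No reference BMI is stated; assuming 20, 22 or 25, that implies a %EWL of about 82, 90 or 104 (18.8/23, 18.8/21, 18.8/18), against 63.7 printed. This uses group means, with baseline on all 75 patients, and is only approximate. It is still enough to require patient-level data before any label is changed.

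Finally, the non-inferiority paragraph might be taken as the real primary analysis. If -10 is read as %EWL points, an assumption, the 90% intervals for A minus B (0.3 to 7.9 and -2.2 to 4.6) both clear it and the disputed label would decide nothing. But the paragraph says the outcome is binary, whereas %EWL is analysed as a mean. The two statements need reconciling, whichever was intended.

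**Conclusion.** The point stands and should be fixed. The protocol assigns no between-group test or effect estimate to its primary outcome, and its only between-group criterion for an outcome is a one-sided binary one that conflicts with the two-sided rule. The omission has a visible consequence: the 12-month significance label for %EWL is not reproduced by the standard two-sided test, even under the most favourable rounding, and two-thirds (10/15) of the P<0.05 labels in Table 3 are not reproduced either.

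The omission rests on the text alone. The p-values assume that the printed means, SDs, counts and group sizes are correct and, for %EWL and BMI, that a t-test is a fair stand-in for the unnamed test. They show that the labels are unsupported as printed, not which entry is in error. The choice between Welch and pooled t-tests, or between Fisher's and chi-square tests, changes no classification. The 138 in the sample-size paragraph plays no part in this check.

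**What to change.** Limit the Wilcoxon sentence to descriptive pre/post changes, and add to section 2.6:

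> Primary analysis: difference in mean %EWL (A minus B) by randomised group at 12 and at 24 months, two-sample t-test, two-sided, each with its 95% CI and the number analysed out of 150. Postoperative counts are compared between groups by Fisher's exact test.

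State openly that this analysis was specified after the results were known; naming it now discloses the method but does not prespecify it. Amend the sample-size paragraph to say that the comparison of mean %EWL is the primary analysis and that the binary non-inferiority statement does not describe it.

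Re-run the Table 2 and Table 3 comparisons from patient-level data. Then either correct the 12-month %EWL label and the unsupported Table 3 labels, or name the test that produced them and correct any misprinted mean, SD or count.

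How to handle the 14 (150 − 136) and 19 (150 − 131) patients without 12- and 24-month data is a separate question that this wording does not settle.

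The cost is a few sentences and a short re-analysis of data already collected. The 12-month significance claim, and several in Table 3, may be lost.

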This study was conducted from January 2015 to November 2017 in the Department of General and Emergency Surgery of "A. Rizzoli" Hospital in Lacco Ameno (Naples, Italy). All the procedures were

performed by the same surgeon. Morbid obesity was preoperatively diagnosed according to the International Federation for Surgery of Obesity (IFSO) guidelines (1). Patients were randomized into 2 groups: Group A (dissection starts at 2 cm proximally to the pylorus and continued along the greater curvature to the left crus) and Group B (dissection starts at 6 cm proximally to the pylorus and continued along the greater curvature to the left crus). Results were obtained at 1 and 2 years follow-up.

Pre-operative evaluation

Preoperative evaluation included anthropometric measurements (height in cm, weight in kg, Body Mass Index(BMI) in kg/m²), comorbidity evaluation [Glycated Hemoglobin(A1c), C-peptide, stimulated C-peptide, Electrocardiography (ECG), echocardiography, lower limbs US color-doppler study, thyroid function profile]. All patients were evaluated for the presence/absence of GERD before surgery. All patients were surveyed about the presence of heartburn and/or regurgitation with a specific questionnaire GERD HRQL questionnaire (6). Each of the 10 questions were rated from 0 (absence of symptoms) to 5 (severe symptoms) for a total score that may range from 0 to 50. Symptoms were defined as absent when patients reported a GERD-HRQL score of 0, mild from 1 to 15, moderate from 16 to 24, and severe from 25 to 50. Patients with GERD-HRQL score >16 was considered positive for GERD;(7). Atypical symptoms were also recorded. All patients underwent upper endoscopy (UE) after 20 days proton pump inhibitors (PPIs) or H2 blockers off, with Helicobacter Pylori(HP) test. When present, HP was eradicated according to Maastricht consensus(8). At UE, esophagitis presence was graded according Los Angeles Classification (9). PPI assumption and symptoms relief was also measured. In case of atypical symptoms and PPI refractoriness, pH-monitoring was indicated to confirm or exclude GERD diagnosis.

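### A paired pre/post test on reflux score or esophagitis grade would be biased toward worsening, because patients were excluded on those same preoperative measurements; the comparison of randomised arms is not affected

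*Combined protocol and SAP*

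**What the plan says.** - **Test.** Section 2.6: "Differences between preoperative and postoperative parameters were compared by Wilcoxon paired rank test". Chi-square and t-tests are assigned to baseline comparisons only. The level is two-sided 0.05, which is 2.5% in each direction.
- **Endpoints.** Section 2.5: "The secondary endpoints were GERD and esophagitis studied with Upper endoscopy and GERD score". Tables 3 and 4 give both measures before surgery and at follow-up.
- **Preoperative measurement.** Pre-operative evaluation: "All patients underwent upper endoscopy (UE) after 20 days proton pump inhibitors (PPIs) or H2 blockers off", and "All patients were surveyed about the presence of heartburn and/or regurgitation with a specific questionnaire GERD HRQL questionnaire". One reading of each is described.
- **Exclusions.** Section 2.2 excludes "GERD with esophagitis scored as or greater than grade B". It also says "GERD was also considered as severe with GERD-HRQL > 30", joined by *and* to interference with daily life or restriction of diet. The end of that sentence is garbled.
- **Result of the exclusions.** Before surgery, Table 4 has no grade B, C or D among 150 patients and Table 3 has no score above 31.

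**The concern.** The preoperative endoscopy and questionnaire serve both as the entry screen and as the baseline of the paired comparison. Some patients who pass a screen do so because that one reading was low for them. Their next reading is higher on average, even with no treatment effect. A paired test against the screening value counts this drift as deterioration, so its null hypothesis of no change is false by selection.

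At stake is any statement that reflux or esophagitis rose significantly after sleeve gastrectomy within an arm, or any new-onset rate read across the columns of Tables 3 and 4. No second baseline, unoperated control or adjustment for regression to the mean is described.

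**Working it through.** The plan gives no figure for this test, so there is none to reproduce. The check is how often the test would report worsening if surgery changed nothing.

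**Inputs from the documents**
- 218 consecutive patients and 150 randomised (section 2.2): 218 - 150 = 68 not randomised. Removal for reflux is therefore at most 68/218 = 31.2%, and that counts every reason.
- Grade A at baseline (Table 4): (4 + 5)/150 = 6%.
- Endoscopy at 1 year (Table 4): 53 and 55 patients, about 54 per arm.
- Grade B or worse at follow-up (Table 4): Group A (11 + 2)/53 = 24.5% and (9 + 1)/52 = 19.2%; Group B 5/55 = 9.1% and 3/53 = 5.7%.

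**Assumptions, not in the documents**
- Share p of screened patients removed for grade B or worse: 2%, 5%, 10%, 15%.
- Correlation r between two endoscopies on the latent severity scale: 0.5, 0.7, 0.9.
- No effect of surgery.

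**Step 1: grade B or worse at follow-up from selection alone.** With a bivariate normal latent severity, let p11 be the probability of grade B or worse at both readings. Then

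P(B or worse later | below B at entry) = (p - p11)/(1 - p).

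Example: p = 0.10 and r = 0.7 give p11 = 0.0468, so (0.10 - 0.0468)/0.90 = 5.9%.

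| p removed | r = 0.9 | r = 0.7 | r = 0.5 |
|---|---|---|---|
| 2% | 0.9% | 1.4% | 1.7% |
| 5% | 1.9% | 3.2% | 4.0% |
| 10% | 3.5% | 5.9% | 7.5% |
| 15% | 4.9% | 8.4% | 10.9% |

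Group A's 24.5% and 19.2% exceed every cell. Group B's 9.1% at 1 year is reached in one cell (15%, r = 0.5), and its 5.7% at 2 years in four.

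**Step 2: behaviour of the test.** Arms of 54 were simulated from the same model with patients at B or worse removed at entry, and grades 0/A/B/C were compared by a two-sided 5% Wilcoxon signed-rank test with ties. Share of no-effect trials declared significantly worse (nominal 2.5%):

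| p removed | r from 0.9 to 0.5 | at r = 0.7 |
|---|---|---|
| 2% | about 3-4% | about 4% |
| 5% | about 4-15% | about 10% |
| 10% | about 10-40% | about 27% |
| 15% | about 16-65% | about 49% |

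Repeat runs differ by up to about 3 points. At the 31% ceiling, with 53 per arm, the range is 54-98%.

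**Step 3: is it the cut or the floor?** With no exclusion but most patients still at grade 0, the rate is about 1-3%. That 150 - 9 = 141 of 150 patients start without esophagitis therefore causes no inflation by itself. The truncation does.

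**Step 4: GERD-HRQL.** A similar simulation with 65 per arm, calibrated to (7 + 9)/150 scoring 16-30 at entry, gives 3-4% false worsening if 2% were removed, 5-7% if 5%, 6-17% if 10% and 17-53% if 20%. It treats the cut at 30 as sharp. The stated rule also needs functional impact, so these figures are if anything high.

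**The case against.** **The plan does not name reflux or esophagitis in the paired test.** True. Section 2.6 says only *parameters*, and section 2.5 uses that word for weight loss. The p-values in Table 3 appear to compare the arms at each visit, Table 4 prints none, and no pre/post p-value is shown. A reader might infer that the trial ran a biased test on these endpoints. The documents show only that the wording permits it. The wording still matters: %EWL and %TWL have no preoperative value to pair, so the measures that fit the sentence are chiefly weight, BMI, GERD-HRQL and esophagitis grade.

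**The size rests on missing inputs.** This stands. The breakdown of the 68 exclusions belongs to Fig. 1, which is not shown, and the test-retest correlation is not given. At 2% removed the per-arm error is close to nominal.

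**An opposing bias exists for endoscopy.** This also stands. The baseline endoscopy followed 20 days off acid suppression, and no such washout is stated after surgery. Treatment at follow-up could lower grades, so the net direction is not certain. That is a further reason not to read the within-arm change as an effect of surgery.

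**The trial's questions concern the arms.** This stands and limits the consequence. Both arms were selected by the same rule before randomisation, and the stated outcomes are between groups.

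**Conclusion.** The point holds, as a minor one. Exclusion on the preoperative endoscopy and questionnaire truncates the baseline, and selection alone biases a paired test on either measure toward worsening. For esophagitis grade, false worsening per arm runs from near nominal (about 3-4% at 2% removed) to 16-65% at 15% removed. This assumes a latent normal severity, correlation 0.9 to 0.5 and no effect of surgery. The true position in that range cannot be fixed from the documents.

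Three stronger readings are not supported:
- That the test will show worsening even if surgery does nothing. At 10% removed and r = 0.7, about 73% of no-effect trials (100% - 27%) would not show it.
- That the esophagitis seen at follow-up is an artefact. Group A's rates exceed every setting in the Step 1 table, and Group B's 1-year rate is matched only at the extreme one.
- That the comparison of 2 cm with 6 cm is compromised. It is not affected by this.

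**What to change.** 1. In section 2.6, limit the paired Wilcoxon test to weight and BMI. The fall in mean BMI is 43 - 25.2 = 17.8 in Group A and 44 - 26.2 = 17.8 in Group B, too large for drift of this kind to matter.
2. For GERD-HRQL and esophagitis grade, name a between-arm test at each visit, for example Mann-Whitney or ordinal regression adjusted for the baseline value, and draw conclusions from that. Removing the paired test without this step would leave both endpoints with no stated analysis.
3. Label within-arm change in these two measures as descriptive.
4. Footnote Tables 3 and 4: grades B-D and severe scores were absent at entry by exclusion, so a rise within an arm does not estimate the effect of surgery.
5. Report how many of the 68 were excluded for grade B or worse and how many for severe GERD.

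The cost is wording, two footnotes and counts from existing screening records. The downside is giving up a within-arm significance claim.

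### Late reflux is reported only as p-value flags that conflict with each other and with their own counts; the GERD-HRQL counts at 12 and 24 months are inconclusive

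*Combined protocol and SAP*

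**What the plan says.** The Background lists among the secondary aims "evaluation of differences in morbidity, mortality, tolerance to food, incidence of reflux symptoms and GERD Health-Related Quality-of-Life (GERD-HRQL) score between the two groups". The pre-operative evaluation section counts a patient as positive for GERD when the GERD-HRQL score is above 16.

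Section 2.6 sets one criterion: "For all tests, a two-sided $p < 0.05$ was considered statistically significant". It assigns chi-square and t-tests to baseline comparisons and a Wilcoxon paired test to changes from before to after surgery. It names no between-group test for reflux at follow-up, no confidence interval, and no size of reflux difference that would matter. The only limit in the plan is in the sample-size paragraph: "THIS IS A CONTROLLED RANDOMIZED STUDY OF BINARY NON-INFERIORITY OUTCOME IN PARALLEL GROUPS", with a confidence limit that "WILL BE ABOVE THE NON-INFERIORITY LIMIT OF -10". That limit has no unit and no named endpoint.

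Table 3 splits the score into three rows: <15, "GERD HRQL Score >16<30" and >31. The flags printed at the late visits are:

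| Row | 12 months, A v B | Flag | 24 months, A v B | Flag |
|---|---|---|---|---|
| <15 | 47/67 v 55/69 | P<0.05 | 49/65 v 55/66 | P<0.05 |
| >16<30 | 16/67 v 13/69 | P>0.05 | 14/65 v 10/66 | P>0.05 |
| >31 | 4/67 v 1/69 | P<0.05 | 1/65 v 0/66 | P<0.05 |

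The column headings add a further flag: P<0.05 at 12 months and p>0.05 at 24 months. Table 4 gives esophagitis grades by group without any p value.

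**The concern.** The 2 cm v 6 cm question weighs weight loss against reflux, so the late reflux comparison matters even as a secondary outcome. As reported, it can be read in two opposite ways. A reader who follows the >16<30 row sees P<0.05 at 3 and 6 months turn into P>0.05 at 12 and 24 months, and may infer that the excess fades. A reader who follows the other two rows sees P<0.05 at every visit and may infer that it lasts. With no row for GERD-positive patients as the protocol defines them, and no differences or intervals, Table 3 cannot show which inference is sound, or whether either is.

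**Working it through.** **1. Inputs.** Counts are from Tables 3 and 4, and the GERD definition (score above 16) is from the pre-operative evaluation section. The 10-point excess in step 5 is my illustration. The plan's own 138 patients cannot be checked or carried over to reflux, because the sample-size paragraph gives neither an endpoint nor a success rate.

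**2. Do the printed flags follow from the counts?** Uncorrected Pearson chi-square on each 2×2 table (Fisher's exact test in brackets):

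| Row | 12 months | 24 months |
|---|---|---|
| <15 | p=0.20 (0.24), printed P<0.05 | p=0.26 (0.29), printed P<0.05 |
| >16<30 | p=0.47 (0.53), printed P>0.05 | p=0.35 (0.38), printed P>0.05 |
| >31 | p=0.16 (0.21), printed P<0.05 | p=0.31 (0.50), printed P<0.05 |

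All four late P<0.05 flags fail. The uncorrected chi-square is the most favourable of the usual tests here, so the choice of test does not rescue them. By contrast, the 3- and 6-month flags in rows <15 (p=0.001 at both visits) and >16<30 (p=0.010 and 0.003) do reproduce.

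**3. GERD-positive patients (rows >16<30 plus >31).**

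- 12 months: A 16+4 = 20/67 = 29.9%; B 13+1 = 14/69 = 20.3%; difference +9.6 points.
- 24 months: A 14+1 = 15/65 = 23.1%; B 10+0 = 10/66 = 15.2%; difference +7.9 points.

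The Newcombe 95% interval, with d = pA − pB and Wilson limits (l, u) per arm, is d − √[(pA−lA)² + (uB−pB)²] to d + √[(uA−pA)² + (pB−lB)²].

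- 12 months: Wilson limits A 20.2 to 41.7, B 12.5 to 31.2; interval **-5.0 to 23.7**, p=0.20.
- 24 months: Wilson limits A 14.5 to 34.6, B 8.4 to 25.7; interval **-5.7 to 21.3**, p=0.25.

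These intervals belong to the combined category, which has no flag in Table 3. The row that prints P>0.05 gives +5.0 (-8.8 to 18.7) and +6.4 (-7.0 to 19.6).

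**4. Do the rows account for everyone?** At 12 months they do: 47+16+4 = 67 and 55+13+1 = 69. At 24 months they do not: 49+14+1 = 64 of 65, and 55+10+0 = 65 of 66. Step 3 counts the missing patient in each arm as GERD-negative. The extremes are 15/65 − 11/66 = +6.4 and 16/65 − 10/66 = +9.5 points. Read literally, the row labels leave scores of 15, 16, 30 and 31 without a row, which may be the cause.

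**5. What could the late comparison detect?** Power of the two-sided 5% chi-square test for a true 10-point excess in Group A, by exact binomial enumeration:

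| Assumed Group B rate | 67 v 69 (12 months) | 65 v 66 (24 months) |
|---|---|---|
| 10% | 37.8% | 36.5% |
| 15% | 31.2% | 30.1% |
| 20% | 27.4% | 26.3% |

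A non-significant result is thus expected about 62% to 74% of the time when such an excess exists.

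**6. Endoscopy (Table 4), esophagitis grade B or worse.**

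- 1 year: 11+2 = 13/53 v 5/55, +15.4 points (Newcombe 95% CI 1.2 to 29.5); p=0.031 uncorrected, 0.058 with continuity correction.
- 2 years: 9+1 = 10/52 v 3/53, +13.6 points (0.7 to 26.8); p=0.035 uncorrected, 0.070 corrected.
- Only 108/150 (72%) and 105/150 (70%) had endoscopy.

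**The case against.** The strongest reply is that there is nothing to misread. No sentence in the documents says that reflux does not last, and four of the six late GERD-HRQL flags print P<0.05 against Group A, so on its face Table 3 points to persisting reflux. This stands in part. A reader might infer from the >16<30 row that the trial clears the 2 cm resection of lasting reflux, but the documents draw no such conclusion, and late reflux is not reported solely as P>0.05. The opposite inference fails as well, because the flags that would carry it do not follow from their counts.

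A second reply is that low power for a secondary outcome is ordinary. That is true, and it is not a reason to enlarge the trial. It is a reason to report an interval instead of a flag.

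A third is that the plan's -10 should not be used as a reflux limit. That also stands. The sample-size paragraph does not attach it to reflux, so the 10 points above illustrate what the numbers could detect and do not serve as a criterion.

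Finally, calling late reflux inconclusive without the endoscopy could understate harm. This is right too: the esophagitis differences point the same way and are larger. They are supportive rather than decisive, since the p values cross 0.05 with continuity correction and nearly 30% had no endoscopy.

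**Conclusion.** The point holds as a reporting and interpretation defect in a secondary harm outcome that should be corrected. Section 2.6 and Table 3 leave late reflux to flags that contradict each other, and four of them contradict their own counts. On the protocol's GERD definition the late excess in Group A is +9.6 points (-5.0 to 23.7) at 12 months and +7.9 points (-5.7 to 21.3) at 24 months. These intervals are compatible with no excess and with one above 20 points.

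This rests on three assumptions: the printed counts are right; patients without late data can be left out, as Table 3 does; and the unclassified patient per arm at 24 months is GERD-negative. Relaxing the last moves the 24-month difference between +6.4 and +9.5 points and leaves it inconclusive. The power range also depends on the illustrative 10 points and on Group B rates of 10% to 20%.

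**What to change.** In 2.6, state that reflux is compared as the A-minus-B risk difference in GERD-positive patients (score above 16), with a 95% CI at each visit, and that P>0.05 is not read as equal reflux.

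In Table 3:

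- Add a separate GERD-positive row with +9.6 (-5.0 to 23.7) at 12 months and +7.9 (-5.7 to 21.3) at 24 months. Do not set these figures beside the >16<30 row, whose own differences are +5.0 and +6.4.
- Correct the late P<0.05 flags in rows <15 and >31.
- Reconcile the unclassified patient in each arm at 24 months, and update that row if the counts change.

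Word the late GERD-HRQL result as inconclusive and report it beside esophagitis grade B or worse: +15.4 (1.2 to 29.5) at 1 year and +13.6 (0.7 to 26.8) at 2 years, with the endoscopy coverage stated. Any claim of no relevant excess needs a reflux limit that the sponsor justifies on its own merits, not the unassigned -10.

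The cost is a short addition to 2.6, a recalculation from printed counts, and a check of two patient records; no new patients are needed. The downside is that several printed P<0.05 flags are lost and the late symptom result becomes inconclusive.
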